Study Procedure	
Participants who meet the diagnostic criteria, inclusion, and exclusion criteria, and have signed the informed consent form will be included in the study. The open-label study period is 4 weeks, including 2 visits: Visit 1 (-1D to 0D) and Visit 2 (4w ± 3d), with no follow-up period.

Evaluation Criteria	
(1) General Information: Demographic data, physical examination, medical history, allergy history, smoking and alcohol history, concomitant medications.
 
(2) Multi-omics Analysis: Including platelet transcriptomics, metabolomics, proteomics, microbiomics.
 
(3) Platelet Function: platelet granule markers (PF4 and <math>\beta</math>-TG), surface activation markers (P-selectin/CD62P, GPIIb/IIIa complex/CD41/CD61), platelet-leukocyte aggregation (CD41 and CD15).
 
(4) Safety Indicators: Routine blood, urine, and stool tests (including occult blood), liver and kidney function tests, ECG, coagulation function, and adverse event recording.

Statistical Analysis Plan	
1. Analysis Data Sets
 
1.1 Full Analysis Set (FAS): Defined according to the ITT principle, including all enrolled participants who received at least one treatment.

1.2 Per-Protocol Set (PPS): Includes participants who met inclusion criteria, completed treatment and follow-up, had medication compliance between 80-120%, did not use concomitant medications affecting efficacy evaluation, had complete main outcome data, and no major protocol violations.

1.3 Safety Set (SS): Includes all enrolled participants who received at least one treatment. Baseline data analysis will be conducted separately for FAS and PPS. Efficacy indicators will be analyzed for both FAS and PPS. Safety and adverse events will be analyzed for SS.

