## 2. Statistical Method Description

2.1 Enrollment Analysis: List the number of enrolled and completed cases, and determine the analysis data sets (PPS, SS).

2.2 Demographic and Baseline Analysis: Descriptive statistics for demographic data and other baseline characteristics: Continuous variables: Calculate the number, mean, standard deviation, median, minimum, and maximum values. Categorical and ordinal data: Calculate frequencies and proportions. Inferential statistical results (P-values) will be listed as descriptive results. Age factors should be considered in data analysis, and data should be stratified or grouped by different age groups.

2.3 Efficacy Analysis: Primary Efficacy Indicators: Evaluate treatment effects through multi-omics analysis and platelet function indicators. Use descriptive and inferential statistical methods such as t-tests, chi-square tests, and Cox regression analysis to compare pre- and post-treatment differences. Secondary Efficacy Indicators: Include safety indicators and adverse event records. Use descriptive statistical methods such as frequency analysis and percentage calculations to describe the incidence and severity of adverse events.

	
2.4 Safety Analysis: Number and rate of laboratory indicators or physical examination abnormalities after treatment. List abnormal laboratory indicators, abnormal physical examination cases, and clinical interpretations.
 
2.5 Laboratory Data: Analyze changes in laboratory test results before and after treatment using paired t-tests or Wilcoxon signed-rank tests.
 
2.6 Adverse Events: Describe the types, frequencies, and severities of adverse events using chi-square tests or Fisher's exact tests for comparisons.
 
2.7 Multiple Comparison Adjustments: For multivariable statistical analyses, use Bonferroni correction or Holm-Bonferroni method to adjust significance levels and control type I error rates.
 
2.8 Critical Assumption Verification: Certain statistical methods require critical assumptions such as normality and homogeneity of variance. Verification methods include: Normality Test: Shapiro-Wilk test or Kolmogorov-Smirnov test. Homogeneity of Variance Test: Levene's test or Bartlett's test. This statistical analysis plan ensures the scientific rigor and reliability of data analysis. All statistical analyses will be performed using SAS or R software by professional statisticians

--	--

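### Does listing adverse events under secondary efficacy commit the trial to a per-protocol adverse-event rate?

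*Combined protocol and SAP*

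**What the plan says.** The points at issue are all in the statistical analysis plan, apart from one line in the Study Procedure.

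- Section 2.3 names the primary indicators as families: "Primary Efficacy Indicators: Evaluate treatment effects through multi-omics analysis and platelet function indicators". It then adds: "Secondary Efficacy Indicators: Include safety indicators and adverse event records". For the latter it asks for frequencies and percentages. It names no analysis set.
- Section 1.3 allocates the sets in two consecutive sentences: "Efficacy indicators will be analyzed for both FAS and PPS. Safety and adverse events will be analyzed for SS".
- Section 1.1 defines the FAS as "including all enrolled participants who received at least one treatment". Section 1.3 defines the SS in the same terms: "Includes all enrolled participants who received at least one treatment".
- Section 1.2 restricts the PPS to patients who, among other things, "completed treatment and follow-up, had medication compliance between 80-120"% and "had complete main outcome data".
- The Study Procedure describes two visits over 4 weeks, "with no follow-up period".

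**The concern.** Adverse events fall under both allocation rules of 1.3: under the first because 2.3 calls them efficacy, and under the second because they are safety data. No sentence says which rule takes precedence. A programmer who followed the 2.3 heading literally could tabulate adverse events in the PPS as well. That set requires completed treatment and adequate compliance, so a patient who stopped because of an event would drop out of the rate meant to count that event. The report could then show two different adverse-event rates, the per-protocol one usually the more flattering.

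Two criteria in 1.2 also look loose. No single main outcome is named, so the requirement for complete data could be read as every omics layer and every platelet marker at both visits, and one failed assay would then remove a patient from all per-protocol results. The PPS also requires completed follow-up in a study that has no follow-up period.

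**Working it through.** **Which rule controls.** The first sentence of the 1.3 allocation is general (efficacy indicators to FAS and PPS). The second is specific: it names safety and adverse events and sends them to SS. The specific rule follows the general one directly, in the section whose job is to allocate sets. Section 2.3 describes indicators and methods and allocates nothing. The natural reading is therefore SS.

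**What changes under the other reading.** FAS and SS have the same membership, so an FAS table would equal the SS table. Only a PPS table could differ, and it would stand beside the SS table without replacing it.

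**How different it could be.** The documents give N = 50 but no adverse-event rate, stopping rate or exclusion rate, so the other inputs are assumptions. Let 10 patients have an event (SS rate 10/50 = 20.0%), let s of them stop, and let k event-free patients be excluded for other reasons. Then

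PPS rate = (10 − s) / (50 − s − k).

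| s | k = 0 | k = 4 | k = 8 |
|---|---|---|---|
| 1 | 9/49 = 18.4% | 9/45 = 20.0% | 9/41 = 22.0% |
| 2 | 8/48 = 16.7% | 8/44 = 18.2% | 8/40 = 20.0% |
| 4 | 6/46 = 13.0% | 6/42 = 14.3% | 6/38 = 15.8% |

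The PPS rate equals the SS rate when k = 40s/10 = 4s, that is, at k = 4, 8 or 16 for s = 1, 2 or 4. On this grid the gap runs from 7.0 points too low to 2.0 points too high. With 5 events instead (SS 5/50 = 10.0%), it runs from 0/45 = 0% if all five patients stop and nobody else is excluded, to 5/45 = 11.1% if none stop and five event-free patients are excluded. The sign and size follow from the chosen inputs, not from anything in the plan.

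**Main outcome data.** Count the platelet markers as one block and the four omics types as four more, at two visits, each block succeeding with assumed probability q = 0.99, 0.98 or 0.95.

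- A rule applied endpoint by endpoint keeps 50q² = 49.0, 48.0 or 45.1 patients.
- Requiring every block keeps the same numbers if failures within a visit are fully shared.
- If half of each block's failure probability is shared across the visit (each block succeeds with probability √q for a visit-wide cause and √q for its own), requiring every block keeps 50q⁶ = 47.1, 44.3 or 36.8.
- If all failures are independent, it keeps 50q¹⁰ = 45.2, 40.9 or 29.9.

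The extra loss at q = 0.95 therefore runs from none to 45.1 − 29.9 = 15.2 patients. With no failure rate in the documents, this range cannot show that the criterion does harm.

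**Follow-up.** The schedule has only a baseline visit and Visit 2 at 4 weeks. Completing follow-up can sensibly mean only attending Visit 2.

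**The case for a change.** The strongest case for a change is that the label is wrong whichever set is used: harms are not efficacy, and once they are taken out 2.3 has no secondary efficacy indicator at all. Sections 2.4 to 2.6 return to safety without naming a set, so they do not settle the overlap. A per-protocol adverse-event rate is not a sound safety figure, and closing the door on it costs only a little wording.

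The criticism of the label stands, and so does the mismatch over follow-up. What does not stand is that either alters a result the trial needs, because the all-treated rate is required by 1.3 in any case.

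The obvious remedy is not free either. Section 2.3 is the only place that asks for adverse-event incidence as frequencies and percentages. Section 2.6 ties its description of adverse events to chi-square or Fisher's exact comparisons, although the trial has one group. Striking adverse events from 2.3 would lose the suitable method. It would also leave ECG, a listed safety indicator that 2.4 to 2.6 do not name, without an analysis.

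Likewise, replacing the data-completeness criterion with endpoint-specific sets would keep more patients per endpoint but leave no single PPS for the baseline table that 1.3 requires. Either choice can be defended.

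**Conclusion.** No change to the plan is called for. The heading in 2.3 is a labelling slip, and the specific SS sentence in 1.3 already puts adverse events in the right population. The only possible effect is one redundant per-protocol table, which no passage explicitly requests, in a single-arm exploratory study of 50 patients. No error rate or sample-size argument depends on it.

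The illustrative gap of 7.0 points too low to 2.0 points too high rests wholly on an assumed 10 patients with events and assumed exclusions.

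The two points on 1.2 touch only the per-protocol results. The first is a missing definition that analysts can supply sensibly before the PPS is fixed. The second is a clerical wording that the visit schedule resolves. This conclusion assumes that the analysts take the specific sentence of 1.3 over the heading in 2.3, as an experienced statistician would.

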## Clinical Research Protocol

Title	Clinical Study and Molecular Mechanism of Xuesaitong Soft Capsule in the Treatment of Acute Coronary Syndrome After Percutaneous Coronary Intervention
Version Number	2024XLA098-2
Responsible Institution	Xiyuan Hospital of China Academy of Chinese Medical Sciences
Target Population	Patients with Acute Coronary Syndrome (ACS) after Percutaneous Target Population Coronary Intervention (PCI), both male and female, aged between 18 and 80 years.
Objective	To interpret the microcosmic manifestations of ACS development using multi-omics technologies, explore key biomarkers and the correlation Objective between disease and syndrome, and elucidate the macro and microcosmic manifestations and biological basis of Xuesaitong soft capsule in the treatment of ACS from multiple perspectives.
Study Design	Single-center, open-label, exploratory clinical study.
Sample Size	50 ACS patients post-PCI in an open-label group.
Study Duration	From October 13, 2024, to December 1, 2026.
Inclusion Criteria	
(1) Patients diagnosed with acute ST-segment elevation myocardial infarction, acute non-ST-segment elevation myocardial infarction, or unstable angina according to Western medical standards. Inclusion Criteria.
 
(2) Within 4 weeks post-PCI.
 
(3) Aged between 18 and 80 years, both male and female.
 
(4) Voluntarily participating in the clinical trial, having signed the informed consent form.

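### Safety is classed as secondary efficacy (2.3), laboratory before/after P-values carry no descriptive label (2.5), and no planned summary separates new laboratory abnormalities from pre-existing ones (2.4)

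*Combined protocol and SAP*

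**What the plan says.** All references are to the combined protocol and SAP.

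- **2.3 Efficacy Analysis:** "Secondary Efficacy Indicators: Include safety indicators and adverse event records". The next sentence reads: "Use descriptive statistical methods such as frequency analysis and percentage calculations to describe the incidence and severity of adverse events".
- **Analysis Data Sets (1.1 to 1.3):** efficacy indicators are analysed on FAS and PPS, and safety and adverse events on SS.
- **2.4 Safety Analysis:** "Number and rate of laboratory indicators or physical examination abnormalities after treatment". It adds: "List abnormal laboratory indicators, abnormal physical examination cases, and clinical interpretations".
- **Section 2.5** gives the method for laboratory values: "Analyze changes in laboratory test results before and after treatment using paired t-tests or Wilcoxon signed-rank tests". No parameter list is given, and nothing is said about how the P-values are to be used.
- **2.7 Multiple Comparison Adjustments:** "For multivariable statistical analyses, use Bonferroni correction or Holm-Bonferroni method to adjust significance levels and control type I error rates".
- **Evaluation Criteria (4), Safety Indicators:** "Routine blood, urine, and stool tests (including occult blood), liver and kidney function tests, ECG, coagulation function, and adverse event recording". Panels are named; analytes are not counted.
- **2.2 Demographic and Baseline Analysis** labels its P-values descriptive. No other section does so.
- **Exclusion criterion 6** removes patients with ALT or AST at or above 3×ULN. Patients below that limit may enter.
- **Sample Size:** "50 ACS patients post-PCI in an open-label group". The design is described as exploratory, and there is no comparator.

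**The concern.** Three weaknesses meet in the laboratory safety data.

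1. **Classification.** Calling safety indicators efficacy gives the same data two sets of instructions about who is analysed. It also opens a route by which a laboratory P-value could be reported as a secondary benefit.
2. **Status of the P-values.** Section 2.5 tests an unlimited list of laboratory results. The plan does not say whether those P-values are descriptive, or whether 2.7 governs them. Some will be small by chance.
3. **Change in individual patients.** Section 2.5 is the only planned analysis of laboratory change, and it looks at the average or rank shift. Section 2.4 looks at individuals, but only after treatment.

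At stake is how the secondary and safety results are reported and read. Feasibility and the primary analysis are not affected.

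**Working it through.** The plan states no alpha, power or expected change, so there is no figure of its own to reproduce.

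**Step 1. Analysis sets.** Sections 1.1 and 1.3 define FAS and SS by the same condition: enrolled and treated at least once. Their membership therefore coincides. The conflict bites on PPS. Under the efficacy label, safety would also be analysed on PPS, which requires completed treatment and 80-120% compliance. A patient who stopped early because of an adverse event would be left out of that analysis. Under the safety instruction that patient is kept.

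**Step 2. Chance findings in 2.5.** Assumptions: two-sided 5%, k = 10 to 40 tested parameters, no true change.

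- Independent tests: P(at least one) = 1 − 0.95^k. For k = 30 this is 1 − 0.95^30 = 0.785, with 30 × 0.05 = 1.5 false positives expected.
- Equicorrelated tests with correlation ρ: P = 1 − ∫ φ(u) [Φ((1.96 − √ρ·u)/√(1−ρ)) − Φ((−1.96 − √ρ·u)/√(1−ρ))]^k du.

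| k | independent | ρ = 0.5 | ρ = 0.8 |
|---|---|---|---|
| 10 | 40% | 29% | 17% |
| 30 | 79% | 51% | 26% |
| 40 | 87% | 57% | 28% |

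The lowest entry is still more than three times the nominal 5%.

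**Step 3. If 2.7 is taken to apply.** Bonferroni over an assumed 30 tests gives 0.05/30 = 0.00167 per test. For a true paired shift of 0.4 SD with n = 50, the noncentrality is 0.4 × √50 = 2.83 on 49 degrees of freedom. Power is 79% at 0.05 and 32% at 0.00167. The shift detectable with 80% power rises from 0.40 to 0.59 SD. Correction would therefore make a non-significant safety result less reassuring.

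**Step 4. What 2.5 can see of individual harm.** Simulation, with all inputs assumed: n = 50, log-change SD 0.2 to 0.4, and a fivefold rise in a few patients.

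- Three such patients: the paired t-test is significant in 15-18% of trials and Wilcoxon in about 9%.
- One or two such patients: both tests reject in about 3-9% of trials, close to the false-positive rate.

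**Step 5. What 2.4 adds and what it misses.** Suppose baseline ALT has median 25 and log SD 0.4, within-patient log SD is 0.3, and the upper limit is 40 to 50 U/L (all assumed). After a fivefold rise the median is 125 and the log SD is √(0.4² + 0.3²) = 0.5. The share above 50 is Φ(ln(125/50)/0.5) = 97%, and above 40 it is Φ(ln(125/40)/0.5) = 99%. Section 2.4 would count and list nearly all of these patients.

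Now compare three hypothetical eligible patients:

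| Patient | Visit 1 ALT | Visit 2 ALT | Counted in 2.4 |
|---|---|---|---|
| A | 2×ULN | 2×ULN | yes |
| B | normal | 2×ULN | yes |
| C | low in the normal range | top of the normal range | no |

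A and B contribute equally to the 2.4 rate, although only B has a new abnormality. A rise such as C's goes uncounted. No planned summary cross-classifies the two visits.

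**The case against.** **Section 2.4 already reports affected patients.** This is the strongest reply. A reader might infer from 2.5 alone that a non-significant mean would hide patients who were harmed. The documents do not support that: 2.4 gives counts and rates and lists abnormal cases with clinical interpretation, and Step 5 shows it would catch large rises. What remains is the missing baseline comparison.

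**Section 2.3 attaches only descriptive methods.** This is partly right. Its sentence on method names adverse events, and 2.3 prescribes no significance test for safety. Laboratory values get their method from 2.5, which is inferential. No section says that a significant laboratory change will be claimed as efficacy. The label permits that reading and does not plan it.

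**The tests may not be uncontrolled.** A reader might also infer that about 30 tests run with no multiplicity control. The documents count no parameters, and 2.7 may be meant to cover them. Occult blood, and commonly other urine and stool results, are categorical and suit neither test in 2.5, so it is not certain that every parameter is tested. The supportable statement is that the scope of 2.7 is undefined.

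**The study is exploratory.** This stands and lowers the severity. With one arm and no confirmatory safety hypothesis, laboratory P-values are signals to examine. That is a reason to label them so. In addition, patients enter within 4 weeks of PCI without a control group, so a real change may reflect recovery or background treatment. Multiplicity correction cannot address that.

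**Conclusion.** The point holds in three limited parts.

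- **Misclassification.** Section 2.3 conflicts with the analysis-set section. This needs no assumption. Its practical effect is an added safety analysis on PPS and the possibility that a laboratory change is presented as benefit.
- **Undefined status of the 2.5 P-values.** They are not labelled descriptive, and the reach of 2.7 is unclear. The chance of at least one false positive is about 17% to 87%, assuming two-sided 5%, 10 to 40 parameters, and correlation between 0 and 0.8.
- **No baseline comparison in individual patients.** Section 2.4 counts only after treatment although abnormal baselines are admitted, and 2.5 detects only an average shift. This follows from the text; the detection rates in Step 4 rest on assumed inputs.

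Severity is minor to moderate, given the exploratory design and the listings in 2.4.

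**What to change.** 1. **2.3:** move safety indicators and adverse events out of the efficacy section, and state that they are analysed on SS only.
2. **2.4 and 2.5:** for each laboratory parameter, add a Visit 1 by Visit 2 shift table (low/normal/high, or normal/abnormal for categorical urine and stool results). Report the mean or median paired change with a 95% CI for continuous parameters.
3. **2.5 and 2.7:** state that any laboratory P-values are descriptive and support no efficacy or safety claim, and that 2.7 does not apply to them.
4. **Interpretation:** state that, without a control arm, laboratory changes cannot be attributed to the drug.

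The cost is SAP wording and one shift-table program on data already collected; no new patients, visits or samples are needed. The downside is that laboratory changes can no longer be reported as statistically significant secondary results.

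### Section 2.6 tests adverse events between groups a one-group study does not have, AE percentages carry no interval, and section 2.4 does not separate new abnormalities from those already present at Visit 1

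*Combined protocol and SAP*

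**What the plan says.** The protocol synopsis describes a single-centre, open-label, exploratory study with one group of 50 patients, all given the same regimen for four weeks. There are two visits: Visit 1 on the day before or the day of starting, and Visit 2 at four weeks, with no follow-up afterwards.

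The SAP treats safety in several places:

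- **Section 1.3** fixes the population: "Safety and adverse events will be analyzed for SS" (the Safety Set, patients with at least one treatment).
- **Section 2.3** is descriptive: "Use descriptive statistical methods such as frequency analysis and percentage calculations to describe the incidence and severity of adverse events".
- **Section 2.4** asks for "Number and rate of laboratory indicators or physical examination abnormalities after treatment" and adds "List abnormal laboratory indicators, abnormal physical examination cases, and clinical interpretations".
- **Section 2.5** covers laboratory change: "Analyze changes in laboratory test results before and after treatment using paired t-tests or Wilcoxon signed-rank tests".
- **Section 2.6** says "Describe the types, frequencies, and severities of adverse events using chi-square tests or Fisher's exact tests for comparisons" and does not say what is compared with what.

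The only grouping of patients in the SAP is in section 2.2: "Age factors should be considered in data analysis, and data should be stratified or grouped by different age groups". It gives no cut-points and does not mention adverse events. No confidence interval is planned anywhere. Exclusion criterion 6 removes patients with ALT or AST at or above 3 x ULN, so milder elevations at entry are allowed.

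**The concern.** A chi-square or Fisher test of adverse events needs at least two independent groups. This design has one, so section 2.6 followed literally is either undefined or is applied to groups chosen after the data are seen. Any resulting p-value says nothing about the safety of the drug.

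What a single group can deliver is the percentage of patients with each event and how precisely it is known. The plan gives the first and omits the second. With 50 patients, a report of no events could be read as no risk.

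The rate in section 2.4 has a different weakness. It is a prevalence at the end of treatment. A reader of a four-week drug study wants to know how many patients became abnormal on treatment, and that rate cannot say.

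**Working it through.** The documents give no safety figure to reproduce: there is no expected AE rate, significance level, power or dropout allowance. The size of the problem is therefore shown with assumed event counts.

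**1. Can the comparison in 2.6 be given a meaning?** There are three candidate readings.

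- *Between treatments:* not possible, since all 50 patients receive the same regimen.
- *Before versus after:* Visit 1 spans only day -1 to day 0, so there is no pre-treatment AE period to set against four weeks on drug. Ordinary chi-square and Fisher tests also assume independent groups, not the same patients twice.
- *Between age groups:* section 2.2 supplies no cut-points and 2.6 does not refer to it. The contrast would compare ages, not assess the drug. For illustration, assume a 25/25 split and two-sided 0.05. With 0/25 versus 5/25, the two-sided Fisher p-value is 2 x C(25,5)/C(50,5) = 2 x 53,130/2,118,760 = 0.0502. Enumerating all tables, the exact power for true rates of 10% versus 30% is 30.5%.

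**2. Precision of an AE percentage.** Input: n = 50 from the synopsis, all assumed to be in the Safety Set. The exact (Clopper-Pearson) two-sided 95% limits for x events are

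- lower = Beta quantile (0.025; x, n - x + 1), taken as 0 when x = 0;
- upper = Beta quantile (0.975; x + 1, n - x).

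For x = 0 the upper limit reduces to 1 - 0.025^(1/50) = 7.1%.

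| Events (assumed) | Percentage | Exact 95% limits |
|---|---|---|
| 0/50 | 0% | 0 to 7.1% |
| 1/50 | 2% | 0.05 to 10.6% |
| 5/50 | 10% | 3.3 to 21.8% |

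**3. What the 2.4 rate conceals.** New-onset rate = (abnormal at Visit 2 and normal at Visit 1) / (normal at Visit 1). Two sets of assumed counts give the same planned figure:

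| | Case 1 | Case 2 |
|---|---|---|
| Abnormal at Visit 1 | 15 | 5 |
| Of these, still abnormal at Visit 2 | 12 | 3 |
| Newly abnormal at Visit 2 | 3 | 12 |
| Rate under 2.4 | (12 + 3)/50 = 30% | (3 + 12)/50 = 30% |
| Normal at Visit 1 | 50 - 15 = 35 | 50 - 5 = 45 |
| New-onset rate (exact 95% limits) | 3/35 = 8.6% (1.8 to 23.1%) | 12/45 = 26.7% (14.6 to 41.9%) |

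The paired tests in 2.5 do not fill this gap. They address the average shift in a laboratory value, do not count patients who crossed into abnormality, and do not cover physical examination.

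**The case against.** The strongest reply is that only the 2.6 wording conflicts with the design, and that the interval and the shift table are additions to a short SAP for an exploratory study with no safety hypothesis. Much of the output is already planned: AE percentages in 2.3, the denominator in 1.3, and a listing with clinical interpretations in 2.4 that is feasible case by case at 50 patients. Anyone given n and N can compute an exact interval. The 2.4 rate is correctly labelled as after treatment and is not wrong in itself. An exploratory age-group comparison is also conceivable, so naming the groups might suffice.

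Some of this stands. The primary analyses are untouched, the 2.4 rate is incomplete, not false, and both 2.4 scenarios are illustrations: the documents do not say how common abnormalities at entry will be. The age example also depends on the split, since the same five events as 0/30 versus 5/20 give p = 0.007.

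It does not remove the point. A test whose groups must be guessed is not prespecified, and an age contrast would still not address the drug's safety. Leaving readers to compute the intervals does not replace planning them when the AE percentage is the main safety result. A listing may note that a finding was pre-existing, but it yields no new-onset rate.

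**Conclusion.** The concern holds in all three parts. The 2.6 test is undefined for this design, or unrelated to the drug if applied to age groups. The AE percentages lack an interval at a sample size where zero events is still compatible with a true rate of up to 7.1%. The 2.4 rate cannot distinguish persistent from new abnormalities: in the assumed cases the new-onset rates differ about threefold (26.7/8.6 = 3.1) behind an identical 30%.

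The intervals assume that all 50 patients enter the Safety Set; fewer would generally widen them. The Visit 1 and Visit 2 counts and the 25/25 age split are assumptions. The conclusions about 2.6 and the missing interval rest on the text alone. This should be corrected, but the consequence is moderate: it affects how the safety results can be read, not the omics or platelet-function analyses.

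**What to change.** **Section 2.6.** Delete the chi-square and Fisher comparisons. Report the number and percentage of Safety Set patients with each adverse event, by severity, with exact (Clopper-Pearson) 95% confidence intervals. This also brings 2.6 into line with the descriptive approach of 2.3.

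**Section 2.4.** Keep the overall post-treatment rate and the case listing. Add Visit 1 by Visit 2 shift tables (normal/abnormal) and a new-onset rate: patients abnormal at Visit 2 among those normal at Visit 1, with an exact 95% confidence interval. Do this for each laboratory test, and for physical examination and ECG where both visits have a record.

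**Cost.** SAP wording and a few extra tables. Section 2.5 already implies laboratory values from before and after treatment. The documents do not state that physical examination and ECG are done at both visits, so those tables depend on confirming it. The one drawback is that wide intervals will make the safety statement look less favourable, though they show fairly what 50 patients can support.
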